8.6.5 Assessment of the age-appropriate formulation acceptability

As per EMA guideline of August 1st 2013[39], the acceptability of febuxostat tablets in children will be assessed through a 5-point hedonic scale anchored with the word super bad and super good [40] immediately after drug intake as reported below:

8.7 ADVERSE EVENT DEFINITIONS, MONITORING/ RECORDING AND MANAGEMENT

8.7.1 Definitions

8.7.1.1 Adverse Event (AE)

Any untoward medical occurrence in a patient or clinical trial subject administered a medicinal product and which does not necessarily have a causal relationship with this treatment.

An AE can therefore be any unfavorable and unintended sign (including an abnormal laboratory finding), symptom, or disease temporally associated with the use of a medicinal product, whether or not considered related to the medicinal product.

8.7.1.2 Drug Relationship

The relationship between an AE and study drugs will be judged according to the following categories:

1. **Certain:** The AE occurs in a plausible time relation to the administration of the drug and cannot be explained by a concurrent disease or other drugs or chemicals. The response to withdrawal of the drug (dechallenge) should be clinically plausible. The event must be definitive pharmacologically or phenomenologically, using a satisfactory rechallenge procedure if necessary.
2. **Probable:** The AE occurs in a reasonable time relation to the administration of the drug, it is unlikely to be attributed to a concurrent disease or other drugs or chemicals and it follows a clinically reasonable response on withdrawal (dechallenge). Rechallenge information (AE reappearance after drug reintroduction) is not required to fulfil this definition.
3. **Possible:** The AE occurs with a reasonable time relation to the administration of the drug, but it could also be explained by a concurrent disease or other drugs or chemicals. Information on drug withdrawal (dechallenge) may be lacking or unclear.
4. **Unassessable:** The relationship cannot be judged, because of the information is insufficient or contradictory and cannot be supplemented or verified.
5. **Unlikely:** A causal relationship cannot be definitively ruled out, but

- other drugs, chemicals, or underlying disease provide plausible explanations and/or
- the temporal relation to the administration of the drug makes a causal relation improbable.

6. **Not Related:** Any of the following are present:

- existence of a clear alternative explanation, and/or
- unreasonable temporal relationship between Drug and Event, and/or
- non-plausibility.

8.7.1.3 Adverse Drug Reactions (ADRs)

ADRs are all untoward and unintended responses to an investigational medicinal product related to any dose administered.

The definition implies a reasonable possibility of a causal relationship between the event and the Investigational Medicinal Product (IMP). This means that there are facts (evidence) or arguments to suggest a causal relationship.

ADRs are considered all AEs for which the relationship is considered as:

1. Certain
2. Probable
3. Possible
4. Unassessable

AEs are not considered as ADRs when the relationship is judged as:

5. Unlikely
6. Not related

8.7.1.4 Seriousness

An AE/ADR is considered Serious when:

- results in death;
- is life-threatening;

NOTE: Life-threatening is considered any AE in which the patient was at risk of death at the time of the event; it does not refer to an event which hypothetically might have caused death if it were more severe.

- requires inpatient hospitalisation or prolongation of existing hospitalisation;
- results in persistent or significant disability/incapacity;
- is a congenital anomaly/birth defect;
- is another medically important condition that may jeopardise the patient or may require intervention to prevent one of the outcomes listed above. Any suspected transmission of an infectious agent via a medicinal product is considered serious and should be assessed under the category of medically important events in the absence of other seriousness criteria.

An AE/ADR is considered **Non-serious** when it does not fulfill the conditions for the definition of Serious AE/ADR.

NOTE: Hospitalization for chemotherapy administration shall not qualify as adverse event.

8.7.1.5 Adverse Event (AE)/Adverse Drug Reaction (ADR) Intensity

The intensity level of a Serious or a Non-serious AE or ADR is attributed according to the following definitions:

- **Mild:** does not interfere with routine activities; in case of laboratory tests, when there is a mild abnormality.
- **Moderate:** interferes with the routine activities; in case of laboratory tests, when there is a moderate abnormality.
- **Severe:** makes it impossible to perform routine activities; in case of laboratory tests, when there is a significant abnormality.

In addition, the Investigator will adopt the NCI-CTCAE v 4.03 (Common Terminology Criteria Adverse Event) for grading each AE (please refer to Appendix V: Common Terminology Criteria for Adverse Events (CTCAE) Version 4.0. Published: May 28, 2009 (v 4.03: June 14, 2010). U.S.Department of Health and Human Services – National Institute of Health – National Cancer Institute for details).

8.7.1.6 Adverse Event (AE)/Adverse Drug Reaction (ADR) Expectedness

An AE/ADR is considered **Unexpected** when the nature, severity, or outcome of the AE/ADR is **not** consistent with the information provided in the Reference Safety Document (the SmPC of ADENURIC® 120 mg and the safety section from the Febuxostat IB, last version available).

8.7.1.7 Serious Unexpected Adverse Drug Reaction (SUSAR)

Any serious adverse event judged by the Investigator or the Sponsor as drug-related (see section 8.7.1.3), and considered as unexpected qualifies as a serious unexpected ADR (SUSAR).

SUSARs are subject to expedited reporting, as specified in section 8.7.3.2, as having a “Reasonable Possibility” of relationship with the IMP.

8.7.2 Monitoring and Recording of Adverse Events

At each visit the Investigator will assess any occurred subjective or objective AE, starting from the informed consent signature to the End of Study Visit (Visit 10, Day 14, ±2days).

AEs communicated by the patient or by the patient’s relatives or delegates through phone calls, letters or emails will also be recorded. In these cases the Investigator will try to obtain medical confirmation and assessment of the occurred AE.

When an AE has occurred, the **Investigator shall record on the respective eCRF-AE recording pages any case, both serious and non-serious, whether or not thought to be drug-related**, observed in or reported by the patient (or relatives/delegates), specifying the judgement on the causal relationship with the study treatment.

Any available information and diagnostic measure (laboratory and instrumental tests, procedures, etc.) shall be recorded in the eCRF.

In addition, if after the end of the study the Investigator becomes aware of any AEs or follow-up in AEs already recorded, this information can be recorded in the eCRF until it is available.

8.7.3 Management of Serious Adverse Events (SAEs)

[figure not shown]
8.7.3.1 Reporting Duties of the Investigator

The Investigator must record all the available information concerning any SAE (whether or not deemed related to the investigational drug) in the corresponding section of the e-CRF, eCRF-AE pages, **no later than 24 hours** after the first knowledge of the occurrence of the event.

Once the information is saved, a notification e-mail will be automatically generated and sent to the Sponsor's DSM, so that the SAE can be retrieved.

The Investigator will be provided with the paper CRF-AE pages to be used only in case of breakdown of the e-CRF System. In such case, the Investigator will be responsible for sending the paper CRF-AE pages form **no later than 24 hours** after the first knowledge and inserting the data in eCRF as soon as the system works again.

Whenever the paper CRF-AE pages are used, they must be submitted by fax or e-mail to the Sponsor's DSM:

For the initial SAE the Investigator should enter at least the following data:

- AE medical term.
- Seriousness criteria.
- Causality assessment.
- Study Code and Patient Identification (patient number) [when the paper CRF-AE pages are used].
- Reporter's name and telephone number for clarification [when the paper CRF-AE pages are used].

If not already reported, the full description of the event and outcome must follow within 1 working day.

In case of **serious cutaneous/hypersensitivity reactions and/or hepatic events**, the Investigator is required to perform any attempt for collecting all the available additional clinical information, by filling in the specific FU forms that will be provided to the Investigator.

The mentioned FU forms duly filled will be sent by the Investigators to the Sponsor's DSM by fax or e-mail, while for the possible photographic documentation the Investigator will contact the Sponsor's DSM for receiving adequate instruction for sending.

The Sponsor's confirmation of reception of the AE report must be kept in the patient's records.

Any questions arise during the processing and medical review of the SAE will be managed by means of electronic queries (i.e. queries in the e-CRF). In case of breakdown of the e-CRF System, queries will be sent by fax or e-mail.

Any information provided by the Investigator as a query reply or as a follow-up AE report will be processed in the same way as the initial AE report within the required timeframe.

When relevant, also the eCRF pages concerning medical history, concomitant medication, and laboratory tests will be retrieved by the Sponsor's DSM.

Any further significant information and supporting documentation that become available (copies of laboratory reports, tests, procedures, autopsy evidence of the cause of death, etc.) shall be provided no later than 24 hours after the knowledge, by the Investigator to the Sponsor's DSM by fax or email.

The Investigator must also comply with the local applicable obligation(s) on the reporting of ADRs to the local concerned Regulatory Authority/Ethics Committee.

8.7.3.2 Reporting Duties of the Sponsor

The Sponsor shall ensure that all relevant information about any suspected serious and unexpected adverse drug reaction (SUSAR), will be expeditiously reported to the competent Authorities (including EudraVigilance Clinical Trial Module for clinical trials for which a EudraCT number has been assigned) and Ethics Committees (following general and local rules and procedures), with these deadlines after the first knowledge, intended as the day when the Sponsor's DSM or CRO receives the notification of the SUSAR:

- Fatal and life threatening unexpected cases, no later than 7 days;
- Other unexpected serious cases, no later than 15 days.

The Sponsor shall ensure that all relevant new information will be also expeditedly reported as follow-up information according to the above mentioned deadlines.

The following safety issues will be subjected to expedited management for the identification of possible necessary actions:

- SAEs associated with the trial procedures;
- Potential clinically significant findings emerging from non-clinical studies;
- An anticipated end or suspension for safety reasons of another trial with the same study drug.

When appropriate and applicable the Sponsor will arrange the adequate information also to the Investigators.

8.7.4 Management of Non-Serious Adverse Events (NSAEs) and/or laboratory abnormalities

The Investigator must record all the available information concerning any NSAE (whether or not deemed related to the investigational drug) in the corresponding section of the e-CRF, eCRF-AE pages, **within 5 calendar days** after the first knowledge of the occurrence of the event.

Once the information is saved, a notification e-mail will be automatically generated and sent to the Sponsor's DSM, so the NSAE can be retrieved

When relevant, also the CRF pages concerning medical history, concomitant medication, and laboratory test will be retrieved by the Sponsor's DSM.

Any further significant information and supporting documentation that become available (copies of laboratory, tests, procedures etc...) shall be provided by the Investigator through additional written reports to the Sponsor's DSM.

In addition, during the clinical trial, abnormalities in laboratory analyses (newly occurring after ICF signature or worsening of previously known abnormalities), which are considered clinically relevant by the Principal Investigator (values significantly above or under normal range or which require an intervention or diagnostic tests, or may result in the IMP discontinuation), should be reported as AEs. However, all abnormalities in laboratory values should be collected and reviewed by Sponsor on a bi-monthly basis.

8.7.5 Management of Pregnancy Exposure Cases

The Investigator is expected to record in the provided "Pregnancy Exposure Report Form" any case of pregnancy exposure occurring in a female patient or in a patient's partner enrolled on the study while participating in the study, occurring during the treatment and follow-up periods. The mentioned form will be sent by fax or email to the Sponsor's DSM within 5 days after the being made aware of the pregnancy.

The "Pregnancy Exposure Report Form" are distributed to the sites to be used for this purpose.

The Investigator is requested to follow each case of pregnancy exposure until the outcome.

If the pregnancy results in an abnormal outcome, this will be recorded in the eCRF as a SAE and managed as above described.

- Incidence of Laboratory TLS (LTLS), from Start of Chemotherapy (Visit 3, Day 3) to the Evaluation Visit (Visit 8, Day 8), based on local laboratory results;
- Incidence and grading of Clinical TLS (CTLs), from Start of Chemotherapy (Visit 3, Day 3) to the Evaluation Visit (Visit 8, Day 8), based on local laboratory results;
- Safety:
 - Incidence, severity (both through Mild/Moderate/Severe scale and NCI-CTCAE grade), seriousness and treatment causality of Treatment Emergent Signs and Symptoms (TESS);

NOTE: An AE is considered as ‘Treatment-Emergent Signs and Symptoms (TESS)’ if it occurs for the first time or if it worsens in terms of seriousness or severity after the first study drug intake (Visit 1, Day 1).

- Frequency of clinically significant abnormalities in physical examination, safety laboratory tests, vital signs and 12-Lead-ECG;
- Change in PS according to Karnofsky/Lansky scale.
- Assessment of the age-appropriate formulation acceptability in children.

9. STATISTICAL METHODS AND DETERMINATION OF SAMPLE SIZE

9.1 DETERMINATION OF SAMPLE SIZE

A sample size of approximately 24 patients should be included in the Pharmacokinetic population for each age and dose group (cohort 1-4, adults). A total of 120 patients was estimated to be sufficient to

Assuming a 10% screening failure rate, approximately 135 patients should be screened in order to obtain the planned total number of 120 patients exposed to treatment.

9.2 ANALYSIS POPULATIONS

- **Safety population:** all patients who received at least one dose of study drug.
- **Pharmacokinetic (PK) population:** all patients who received at least one dose of study drug and have a reliable drug plasma concentration measurement relevant for the pharmacokinetic parameter of interest.
- **Intention to Treat (ITT) population:** all patients allocated to a treatment box.
- **Per Protocol (PP) population:** all patients of the ITT population excluding those who experienced major protocol violation(s).
- **Per Protocol PK (PP-PK) population:** all patients from PK population who do not have any major protocol violation(s) relevant for PK analyses.

9.3 STATISTICAL ANALYSIS

9.3.1 Descriptive statistics

[figure not shown]
[figure not shown]
All study variables will be presented by dose and age group, by using the appropriate descriptive statistics according to the variable nature, unless otherwise specified:

[figure not shown]
- Continuous variables: number of non-missing observations, mean, standard deviation, standard error of the mean, minimum, median, maximum.
- Categorical variables: number of non-missing observations and column percentages (N, %).

9.3.2 Population Pharmacokinetic (Pop-PK) analysis

The plasma concentration data will be analyzed in children, adolescent and adults by nonlinear mixed-effects modeling methods. These methods give both estimates of the population pharmacokinetic parameters and their measures of variability, along with estimates of each patient's parameters.

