As children and adolescents do not show any major differences in TLS diagnosis, management or treatment in respect of the adult population, the FLORENCE study results in adults strongly suggest that febuxostat could be of significant benefit also in children and adolescents. Starting from the assumption that the clinical condition of hyperuricemia in patients with hematological malignancies undergoing chemotherapy is similar between adults and children, it is reasonable to assume that the exposure-response (ER) relationship between the two populations could be similar. In this context, the present study aims at showing that the febuxostat exposure levels achieved in children and adolescents with the selected doses are similar to those achieved in adults receiving 120 mg febuxostat once daily. The proposed Pharmacodynamic (PD) assessment, namely AUC sUA Days 1-8, corresponds to the primary efficacy parameter which was evaluated in the phase III pivotal study FLORENCE in adults [8]. The Pharmacokinetic (PK) and PK/PD modeling and simulation analyses will apply to the PK and PD observed data in order to investigate the relationship between PK/PD and age as main covariate. Therefore, the efficacy and safety data collected in the pivotal phase III study FLORENCE in adults will be bridged to the pediatric population by solely PK, as well as by PK/PD analyses, showing a full matching of febuxostat drug exposure and exposure/response between the adult and pediatric populations.

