8.6.2 Assessment of Pharmacokinetics/Pharmacodynamics

8.6.2.1 Pharmacokinetic parameters

Pharmacokinetic parameters will be calculated from the plasma concentration data using a limited sampling model with nonlinear mixed-effects modeling methods.

A list of parameters that can be estimated according to the PK structural model are defined in Table 2 below. Additional PK parameters may be estimated [REDACTED]

Methods for PK parameters estimation are described in section 9.3.2.

[figure not shown]
Table 2. Pharmacokinetic parameters

C_{max}	Maximum plasma concentration
T_{max}	Time to C_{max}
Vd/F	Apparent volume of distribution
CL/F	Apparent clearance
Ka	Absorption rate constant
$AUC_{(0-t)}$	The area under the plasma concentration versus time curve from time 0 to time of the last quantifiable concentration
$AUC_{(0-\tau)}$	The area under the plasma concentration versus time curve over the dosing interval, where tau is the length the dosing interval (24 hours)
$AUC_{(0-\infty)}$	The area under the plasma concentration versus time curve from time zero to infinity

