9.3.3 Primary analysis

All pharmacokinetic results (e.g., PK parameters and plasma concentrations) will be summarized by dose and age group using appropriate graphs and descriptive statistics (i.e., number of patients (n), mean, standard deviation (SD), geometric mean, 95% confidence intervals, coefficient of variation (CV%), median, minimum, and maximum).

Relevant PK parameters (e.g., AUC, C_{max}) in children and adolescents will be descriptively compared to those in adults to demonstrate sufficient similarity of febuxostat pharmacokinetics.

The primary analyses will be conducted on the PK population and for exploratory reasons on the PP-PK population.

[figure not shown]

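### Group SDs and 95% CIs computed from individual mixed-model estimates of AUC and Cmax are too narrow, mainly for Cmax; take the paediatric/adult contrast from the population model instead

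*Combined protocol and SAP*

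**What the plan says.** Section 8.6.2.1 gives the source of the parameters: "Pharmacokinetic parameters will be calculated from the plasma concentration data using a limited sampling model with nonlinear mixed-effects modeling methods". It refers to 9.3.2 for the estimation method. The visible part of 9.3.2 names nonlinear mixed-effects modelling for children, adolescents and adults, says of it "These methods give both estimates of the population pharmacokinetic parameters and their measures of variability", and continues: "along with estimates of each patient's parameters".

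Section 9.3.3 is the primary analysis: "All pharmacokinetic results (e.g., PK parameters and plasma concentrations) will be summarized by dose and age group using appropriate graphs and descriptive statistics". The statistics listed there are n, mean, SD, geometric mean, 95% CI, CV%, median, minimum and maximum. AUC and Cmax "in children and adolescents will be descriptively compared to those in adults to demonstrate sufficient similarity of febuxostat pharmacokinetics". The visible text defines no paediatric/adult ratio, no interval for one and no similarity margin.

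Section 8.6.2.2.1 sets the sampling: seven troughs (Visits 2 to 8) and four post-dose samples on Day 7, in windows 0.5-2, 2-4, 4-6 and 6-8 h. Section 9.2 admits to the PK population any treated patient with a reliable concentration relevant to the parameter in question. The study rationale (6.1) says the modelling will "investigate the relationship between PK/PD and age as main covariate".

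**The concern.** Read together, 8.6.2.1, 9.3.2 and 9.3.3 compute SDs and confidence intervals from individual model estimates as though each were a measured AUC or Cmax. An individual estimate from a mixed model is a compromise between the patient's data and the value the model predicts for such a patient. The less the data say, the closer the estimate lies to the prediction. The estimates therefore vary less between patients than the true values do, and an interval built from that reduced spread is too short.

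This bears on the primary analysis, which is meant to support similar exposure and, through 6.1, to carry adult efficacy and safety over to children. Compressed CV% and maxima matter too. The doses were selected so that exposure would not exceed that seen in adults at 240 mg (6.3 and 8.2), which is a question about the upper end of the distribution.

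**Working it through.** **The plan's own figure.** The plan states no shrinkage, variance or margin. Its one reproducible design figure is the number to screen: 120 / (1 - 0.10) = 133.3, so 134, against approximately 135. It agrees but does not bear on this point.

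**Why the interval is too narrow.** Take one group of n patients on the log scale.
- True values have SD ω. Each patient's own data give a value y with error SD δ. Let B = ω² / (ω² + δ²), and let m be the group mean of y.
- Individual estimate = m + B(y - m). Its SD is B√(ω² + δ²) = √B·ω. With shrinkage s defined as 1 minus (SD of estimates / true SD), 1 - s = √B.
- Naive SE of the group mean = √B·ω/√n. Actual SE of m = √(ω² + δ²)/√n = ω/(√B·√n).
- Naive width / proper width = B = (1 - s)².

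At s = 10% this is 0.90² = 0.81. At s = 20% it is 0.80² = 0.64. With n = 24, coverage of a nominal 95% interval is about 89% and 80%. The group mean itself is unbiased here; only its stated precision is wrong.

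**How much shrinkage to expect.** This was simulated with individual (MAP) estimates from a one-compartment oral model.
- From the documents: the sampling scheme above; CL/F = 80 mg / 7.5 µg·h/mL = 10.7 L/h (Appendix II, 80 mg SmPC, 5.2, renal impairment); V/F of 50 or 75 L, from the 29-75 L range given there.
- Assumed: Ka 1.5/h; between-patient SD on the log scale 0.2-0.5 for CL, 0.3 for V and 0.8 for Ka; residual SD 0.2-0.5. Population values were treated as known.

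| Samples used | Parameter | Shrinkage | SD relative to true (1 - s) | CI width relative to proper (1 - s)² | Approximate coverage |
|---|---|---|---|---|---|
| All 11 | AUC | 2-23% | 0.77-0.98 | 0.59-0.96 | 76-94% |
| All 11 | Cmax | 13-30% | 0.70-0.87 | 0.49-0.76 | 68-87% |
| Troughs only | AUC | 10-35% | 0.65-0.90 | 0.42-0.81 | not tabulated |
| Troughs only | Cmax | 51-80% | 0.20-0.49 | 0.04-0.24 | not tabulated |

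Widths in the first two rows use unrounded shrinkage. Cmax fares worse because only the 0.5-2 h window covers the labelled tmax of 1.0-1.5 h. The troughs-only rows describe a group made up entirely of such patients. A real cohort would contain only some, chiefly those withdrawn before Day 7.

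**Is the ratio itself biased?** Dose ratios to adults are 40/120 = 0.33, 60/120 = 0.50, 80/120 = 0.67 and 120/120 = 1.00. Central case: CL SD 0.3, residual SD 0.4, V 50 L, all 11 samples, assumed weights 30/55/70 kg with allometric CL and V.

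| AUC ratio to adults | Cohort 1 | Cohort 2 | Cohort 3 | Cohort 4 |
|---|---|---|---|---|
| True | 0.63 | 0.95 | 0.81 | 1.19 |
| Estimated, age/size in model | 0.62 | 0.94 | 0.81 | 1.19 |
| Estimated, no age/size effect | 0.50 | 0.76 | 0.76 | 1.12 |

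With the covariate, the ratio of geometric means is essentially right. Without it, CL/F is drawn towards one common value, so each AUC ratio moves towards the dose ratio. In this example Cohorts 1 to 3 move away from 1, and only Cohort 4 moves towards it.

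**The case against.** **Bias towards similarity.** A reader might infer that shrinkage pulls the paediatric/adult ratio towards 1 and so favours a finding of similarity. The documents do not support this. Shrinkage acts on CL/F, V/F and Ka, not on the ratio. Section 6.1 names age as the main covariate, and with age or size in the model the ratio is nearly unbiased. Without it, the AUC ratio moves towards the dose ratio, which is 1 only for Cohort 4. What remains is that the visible text speaks of investigating age and does not say the effect will be kept whatever its estimate. A bias of either sign is therefore possible if it is dropped.

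**Shrinkage ignored.** A reader might also infer that the sponsor has overlooked shrinkage. That cannot be asserted. FOCE and OBJF stand in the glossary but not in the visible body, and 9.3.2 is very short for the section to which 8.6.2.1 refers for methods. Redacted text may cover diagnostics or a model-based contrast, and 9.5 leaves detail to a SAP. Against this, visible 9.3.3 positively states a descriptive comparison of summarised parameters.

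**No decision rule.** The visible plan has no margin, test or ratio interval, so no formal error rate is affected. This is correct and limits the point to the stated precision of group summaries. Those summaries are nevertheless the visible evidence for similarity.

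**Sampling is not sparse for AUC.** Eleven samples per patient is reasonable for AUC, and some scenarios show almost no shrinkage. The objection is weaker for Cmax. Section 9.2 may already exclude patients without a concentration informative for Cmax, but the visible text does not define what counts as relevant.

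**Conclusion.** The point holds for the spread and the intervals. If 9.3.3 is carried out as it reads, SDs, CV%, ranges and 95% CIs of individual estimates will understate variability and uncertainty. The effect is small to moderate for AUC, clearer for Cmax, and greatest for Cmax in patients without Day 7 post-dose samples. The relation (1 - s)² is exact in the linear-normal case and does not depend on the simulation.

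The size of s does depend on it. The percentages rest on assumed variances, residual error, Ka and a one-compartment form, and are illustrative; the ends of the ranges are good to a few percentage points at best. The simulated half-lives, 0.693 × 50/10.7 = 3.2 h and 0.693 × 75/10.7 = 4.9 h, fall just below the labelled 5-8 h.

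The point does not extend to a general bias of the ratio, or to a claim that shrinkage is left unhandled. It is a weakness in how the primary results would be reported, worth correcting before database lock, and not a flaw in the design or the data to be collected.

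**What to change.** In 9.3.3 (or in the SAP foreseen in 9.5, if redacted text does not already do this):

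- Estimate each cohort-versus-adult ratio of AUC and Cmax, with its 95% CI, from the population model, with the age/size or cohort effect retained whatever its estimate. For AUC, which follows from dose and CL/F, the model SE is enough. Cmax is a function of CL/F, V/F and Ka, so use simulation with parameter uncertainty or a bootstrap.
- Label SDs, CV%, ranges and CIs of individual estimates as descriptive only.
- Report shrinkage by age group for CL/F, V/F and Ka.
- Limit individual Cmax summaries to patients with Day 7 post-dose samples, and say in 9.2 what makes a concentration relevant to Cmax.

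This needs no new samples, visits or patients. The cost is SAP wording, some extra modelling output and somewhat wider stated intervals.
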